5.2 Hypotheses

VIPVIZA has three distinct, but complementary hypotheses:

- Direct viewing of a pictorial representation of asymptomatic atherosclerotic disease, assessed with carotid ultrasound, has the potential to identify individuals at high risk of CVD with higher precision than conventional risk factor-based statistical models.
- The clear understanding of an image of arterial disease during an early asymptomatic phase is of superior value in optimizing adherence to clinical preventive management for both physicians and patients: "A picture speaks a thousand words".
- The resulting preventive management will improve the control of premature CVD.

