6.1 Objective

To assess the impact of a visual image and pictorial report, seen and discussed by both physician and patient, for improving guideline adherence and patient perception and understanding of the CVD risk and consequent motivation for prevention. The extent of the impact is assessed by differences between randomization groups in Framingham Risk Score and SCORE as well as changes in these scores after one and three years. Differences between groups will also be evaluated by risk factor assessment and a further scan after three years to determine disease progression, and a comparison of the prevalence of acute events and mortality at five and 10 years.

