6.2 Specific aims

1. To assess the prevalence of asymptomatic atherosclerotic disease in men and women through identification of carotid plaques and measurement of CIMT, and to relate plaques and CIMT to clinically estimated CVD risk factors.
2. To assess the impact of pictorial representations of atherosclerosis on quality of life, preventive measures, risk factor control and progress of atherosclerotic disease over the course of three years.
3. To explore the impact of pictorial representations of atherosclerosis, as a low-intensive preventive intervention, on physicians' and patients' risk perception, communication and attitudes to CVD prevention.
4. To evaluate how individuals' health literacy and coping strategies relate to CVD risk at baseline, attitudes to screening, risk perception and preventive measures.
5. To investigate biomarkers in relation to CIMT and plaques at baseline, changes in conventional CVD risk markers and lifestyle, and progression of atherosclerosis.
6. To assess the impact of the pictorial representation of atherosclerosis by carotid ultrasound on premature CVD morbidity and mortality over the course of 5 and 10 years.

7. Endpoints

7.1 Primary endpoints:

- 7.1.1 SCORE (22)
- 7.1.2 Framingham risk score (23)

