7.2 Secondary endpoints

- 7.2.1 CVD risk factors (blood pressure, serum cholesterol, LDL, HDL, triglycerides, fasting glucose, HbA1c)
- 7.2.2 Lifestyle (physical activity, tobacco use, alcohol use, eating habits)
- 7.2.3 Ultrasound results (CIMT, presence of plaque, quantitative and qualitative plaque parameters, presence and degree of significant stenosis)
- 7.2.4 Pharmacological treatments of hypertension, dyslipidemia and diabetes, prescriptions and purchases
- 7.2.5 Biochemical biomarkers
- 7.2.6 Clinical endpoints: Hospitalizations due to CVD, diagnostic and therapeutic revascularization procedures (PTCA, PCI, stent) regarding atherosclerotic disease and deaths (all-cause and CVD-specific), as specified in Appendix 2: VIPVIZA diagnoses clinical events and causes of deaths
- 7.2.7 Quality of life.

[figure not shown]
8 Project description

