13.2.3 Summary of planned analyses

The differences in primary outcomes (SCORE risk and Framingham Risk Score) at one year between the treatment groups will be measured and analysed using t-test, for a detailed statistical analyses plan see Appendix 4. As the group sizes are large (more than thousand), it is valid to assume normal distribution of the error around the mean value estimates in both the intervention and the control group. A two-sided p-value <0.05 will be regarded as statistically significant. Complementary to the absolute difference in the Score and the statistical testing of hypotheses, Cohen's effect size will be derived for the difference in mean outcome values divided by a pooled standard deviation of the Score between the 2 groups.

In sensitivity analyses, we will conduct a linear regression covariate-adjusted analysis. We will use the continuous form of the primary outcomes (SCORE risk and Framingham Risk Score) as outcome in the

regression analysis. We will assess the effects of the intervention independently for each of the outcome measures. As many of the baseline co-variates (including sex and age) are related to the prognosis of outcomes, adjustment of pre-defined covariates in the regression analysis might yield in adjusted coefficients which are slightly further from 1.

We will also analyze the changes of SCORE and FRS from baseline to 1-year follow-up and use regression methods to identify predictors of the changes in the scores.

Since patients are recruited into the study during three years from mid-2013 to mid-2016, any change in physicians' prescribing behaviour over the course of the study will be evaluated by comparing prescriptions issued for lipid-lowering and anti-hypertensive medication to participants recruited during the first, second and third years.

Similar statistical methods will be applied for evaluation of the three-year results. At that time point also changes in plaque distributions and IMT variables including differences between intervention and control group will be evaluated.

In long-term, adding risk communication using visualisation of carotid ultrasound results will be compared to routine CVD risk assessment and control within the primary health care setting in hospitalisation due to stroke, myocardial infarctions and revascularisations (at 5-year and 10-year) and reducing overall mortality and cause-specific mortality due to myocardial infarctions and stroke (at 5-year and 10-year) compared to.

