Simple survival curves will be established using Kaplan-Meier curves for CVD mortality and morbidity at 5 and 10 years of follow up comparing the intervention to the control group. Thereafter, predictive Cox Proportional Hazard models will be developed to estimate the overall predictive ability of CIMT, plaque and risk factors on CVD morbidity and mortality at 5 and 10 years in the control group and in the intervention group, taking into account time at risk for disease and deaths. Receiver Operating Characteristic Curves (ROC) will be calculated by estimating the Area Under the Curve (AUC) to ensure the highest possible sensitivity and specificity of the predictions. Confirmatory and exploratory statistical modelling will establish relationships between the intervention and intermediate and mediating factors and variables' relative contribution to explain changes in the outcome variables.

Since participants are recruited into the study during the three years from mid-2013 to mid-2016, any change in physicians' prescribing behaviour over the course of the study will be evaluated by comparing prescriptions issued for lipid-lowering and anti-hypertensive medications among participants recruited during the first, second and third years.

As a basis for how to build regression models Causal diagrams (directed acyclic graphs - DAGs) will be established and causal mediation analysis will be undertaken to illustrate the impact of social, gender, psychological and environmental factors by biomedical risk indices on CVD morbidity and mortality.

Health economic modelling studies will be performed for evaluation of cost-effectiveness. Interviews with participants and physicians will be transcribed verbatim and analyzed using Qualitative Content Analysis (52).

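### For CVD events and deaths (hypothesis 3, aim 6) the supplied documents name only Kaplan-Meier curves between arms, with no effect measure, test or confidence interval

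*Protocol*

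**What the plan says.** Hypothesis 3 (Protocol 5.2) reads "The resulting preventive management will improve the control of premature CVD". Aim 6 (6.2) is "To assess the impact of the pictorial representation of atherosclerosis by carotid ultrasound on premature CVD morbidity and mortality" over 5 and 10 years. The secondary endpoints (7.2) include "Clinical endpoints: Hospitalizations due to CVD, diagnostic and therapeutic revascularization procedures" and deaths.

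A comparison between arms is announced twice without a method. Section 6.1 promises "a comparison of the prevalence of acute events and mortality at five and 10 years". Section 13.2.3 says that "adding risk communication using visualisation of carotid ultrasound results will be compared to routine CVD risk assessment and control" with respect to hospitalisations and deaths, and that sentence then breaks off unfinished.

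Section 13.2.3 then names the method for the arm comparison: "Simple survival curves will be established using Kaplan-Meier curves for CVD mortality and morbidity at 5 and 10 years of follow up", set out for intervention against control. The Summary (section 4) repeats it. The next sentence of 13.2.3 says that "predictive Cox Proportional Hazard models will be developed to estimate the overall predictive ability of CIMT, plaque and risk factors", in the control group and in the intervention group.

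The supplied SAP document is Amendment 2. It covers risk scores, risk factors and ultrasound at 6 years, and does not deal with clinical events.

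**The concern.** A Kaplan-Meier plot by arm is a description. It does not give an estimate of the difference between arms or an interval for that difference. For the primary outcomes, section 13.2.3 supplies a t-test, a standardised effect size and a covariate-adjusted sensitivity analysis. For events, nothing comparable is stated.

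Two risks follow. Overlapping curves may be read as no effect when the data cannot exclude a useful reduction, or a visible gap may be read as an effect with no measure of its uncertainty. Also, if the estimator, covariates and time point are not fixed in advance, they can be chosen after the register data are seen.

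A smaller technical matter is that Kaplan-Meier for CVD outcomes treats deaths from other causes as censoring, which overstates cumulative CVD risk.

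**Working it through.** **1. What each planned events analysis delivers**

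- Kaplan-Meier curves: survival by arm. No contrast, test or interval is stated.
- Cox models: predictive ability of CIMT, plaque and risk factors. Arm is not a listed term.
- ROC/AUC: accuracy of those predictions.
- Causal mediation on CVD morbidity and mortality: the exposures named are social, gender, psychological and environmental factors, not arm.
- Confirmatory and exploratory modelling: links the intervention to mediating factors and to changes in outcome variables. No arm effect on events is named.

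**2. The plan's own sizing figure**

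Section 13.1 sizes the trial on CIMT: SD 0.2, difference 0.02, 1500 per group, 15% drop-out, 3500 in total. The detectable difference is (1.960 + 0.842) × 0.2 × √(2/1500) = 0.0205, against 0.02 stated. The total is 3000/0.85 = 3530, against 3500 stated. Both reproduce closely. No event count, event rate or hazard ratio appears anywhere, so for aim 6 there is no planned figure to check.

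**3. Precision of an arm hazard ratio**

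Inputs: 3532 participants (amendment to Protocol 4.0, item A), equal allocation (12.1) and two-sided 0.05 (13.2.3). Cumulative incidence is an assumption, taken over 2-10%.

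Formulas: d = 3532 × incidence; SE(log HR) = 2/√d; 95% factor = exp(1.96 × SE); power = Φ(|ln 0.80|/SE − 1.96); smallest HR detectable with 80% power = exp(−2.802 × SE).

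| Assumed incidence | Events | SE | 95% factor (÷ and ×) | Detectable HR | Power at HR 0.80 |
|---|---|---|---|---|---|
| 2% | 71 | 0.238 | 1.59 | 0.51 | 15% |
| 3% | 106 | 0.194 | 1.46 | 0.58 | 21% |
| 5% | 177 | 0.150 | 1.34 | 0.66 | 32% |
| 8% | 283 | 0.119 | 1.26 | 0.72 | 47% |
| 10% | 353 | 0.106 | 1.23 | 0.74 | 55% |

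For example, at 5% an observed hazard ratio of 0.85 would have an interval of 0.85/1.343 to 0.85 × 1.343, or 0.63 to 1.14. For 80% power at 0.80, the events needed are 4 × (1.960 + 0.842)²/(ln 0.80)² = 631, which is 631/3532 = 17.9% of participants.

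**4. Size of the competing-risk error**

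Assume a CVD hazard of 1% a year and other deaths at 0.6% a year, over 10 years. One minus Kaplan-Meier is 1 − exp(−0.10) = 9.52%. Cumulative incidence is (0.01/0.016) × (1 − exp(−0.16)) = 9.24%. The gap is 0.28 percentage points, or 3% in relative terms.

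**5. What a 5- or 10-year contrast would estimate**

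The SAP amendment states that controls received their ultrasound result directly after the 3-year visit, that the arms are then no longer parallel, and that later direct comparisons cannot estimate the intervention effect. On a clock from the first scan, about 2 of 5 years and 7 of 10 years fall after that point. A single hazard ratio over the whole period would mix two regimes.

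**6. Time origin**

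The Summary counts 10 years from the first ultrasound. Section 11.8.4 counts 5 and 10 years from the last. Section 14.5 adds 10 register years after visits end in June 2019, which reaches June 2029, yet closes the study on 31 December 2026.

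**The case against.** The strongest reply is that the estimator is unspecified, not ruled out. Section 13.2.3 is a summary and points to Appendix 4 for detail, although it does so in the sentence on the one-year outcomes. The SAP amendment relies on an original plan that was not supplied. Sections 6.1 and 13.2.3 announce arm comparisons, section 13.2.2 implies that event differences will be analysed statistically in due course, and the Summary applies intention-to-treat to secondary outcomes. All of this stands. A reader might infer that no arm effect on events will ever be estimated, and the documents do not support that. Intention-to-treat is nevertheless a principle and not an estimator, and none of the announcements names a measure.

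Four other stronger readings also fail:

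- **The Cox models are fitted strictly within each arm.** This is the natural reading, but the sentence does not exclude a joint model.
- **Low power is the defect.** The figures in step 3 rest on an assumed event rate and describe any arm comparison in this trial, whether or not the text is changed. They show why an interval is needed; they do not measure the omission.
- **Kaplan-Meier seriously distorts the result.** The error is about 0.3 percentage points at assumed rates, would be similar in both arms, and does not arise for all-cause mortality.
- **One 10-year hazard ratio would settle aim 6.** It would not, because controls are informed after year 3.

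It can also be said that Kaplan-Meier estimates may carry standard intervals. Those describe each arm's curve and not the difference between arms.

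**Conclusion.** The point holds in a limited form. In the supplied documents, simple Kaplan-Meier curves are the only method named for comparing CVD events and deaths between arms. The Cox models are prognostic and do not list arm, and no effect measure, test or interval is specified for the randomised contrast. As stated, the analysis gives aim 6 no effect size.

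This concerns secondary endpoints and leaves the primary analyses untouched. It is worth correcting because a cheap and better analysis is available, and because the comparison is likely to be imprecise across the whole assumed range of 2-10% incidence. The conclusion is conditional on Appendix 4 and the original SAP, which could not be checked.

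**What to change.** In section 13.2.3, state the following:

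- **Analysis set and model.** Time to first CVD event and time to death, by randomised arm, in all randomised participants not excluded under 10.2.2. Use a Cox model with arm as the exposure, adjusted for baseline age group and sex.
- **Results.** The hazard ratio with 95% CI, and the 5- and 10-year risk differences with 95% CI. Present the intervals as the main result.
- **CVD outcomes.** Replace one minus Kaplan-Meier with cumulative incidence, treating non-CVD death as a competing event.
- **Interpretation.** Label the 5- and 10-year contrast as early versus delayed information. Do not assume a constant hazard ratio; for example, report the periods before and after year 3 separately.
- **Time origin.** Choose one, and reconcile the Summary, 11.8.4 and 14.5 with it.
- **Prediction.** Keep the Cox and ROC work as a separate analysis.

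The cost is about a paragraph of text. The register data are already planned in 11.8.4, so no new collection is needed. If Appendix 4 or the original SAP already specifies the estimator, a cross-reference would cover that part, but the post-year-3 interpretation and the time origin would still have to be stated consistently.

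### The event-prediction analysis, as described, has no model without imaging and no validation step, so it cannot answer hypothesis 1

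*Protocol*

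**What the plan says.** Protocol 5.2 states as the first hypothesis that an image of asymptomatic disease "has the potential to identify individuals at high risk of CVD with higher precision than conventional risk factor-based statistical models". The Summary (section 4) repeats it.

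The matching analysis is in Protocol 13.2.3. After Kaplan-Meier curves by arm, Cox models are to be developed to "estimate the overall predictive ability of CIMT, plaque and risk factors on CVD morbidity and mortality at 5 and 10 years". Both arms are named as the setting for these models: "in the control group and in the intervention group, taking into account time at risk for disease and deaths". ROC curves are then to be "calculated by estimating the Area Under the Curve (AUC) to ensure the highest possible sensitivity and specificity of the predictions". The Summary gives the Cox models in short form.

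Three other places bear on the point:

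- Aim 1 in Protocol 6.2 is to "relate plaques and CIMT to clinically estimated CVD risk factors". That is an association between measurements and says nothing about later events.
- Protocol 13.2.3 says "for a detailed statistical analyses plan see Appendix 4", in the sentence on the one-year t-test of SCORE and Framingham. Appendix 4 is not among the documents available.
- SAP Amendment 2 covers risk scores, risk factors and ultrasound outcomes at six years. It contains no prediction of events and relies on the original plan for outcome variables and populations.

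**The concern.** The hypothesis is about a difference in precision, while the analysis estimates the level of one quantity, the discrimination of imaging and risk factors taken together. Neither document names a model without imaging, an established score used as comparator for events, a difference in AUC, a test of added value, calibration, or any internal or external validation. A good combined AUC could come entirely from age, blood pressure, lipids and smoking.

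The second issue is optimism. The models are developed in the trial's own data, and nothing is said about correcting the AUC for that. There are many candidate imaging variables: CIMT as maximum, minimum and mean (12.2.1), at several positions and angles on both sides (11.5), and plaque presence, area and texture (11.5). Section 11.5 also says that there is no consensus on which IMT measure to use and plans exploratory work on the choice. Events may be few, since 13.2.2 describes a low to intermediate risk population.

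At stake is whether the long-term report can support a claim that imaging stratifies risk better than current models. The randomised comparison is not affected.

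**Working it through.** **Reproduction.** The documents give no AUC, expected event count or number of predictors for these models, so there is no figure of the plan to reproduce.

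**Inputs from the documents.** 3532 participants included (Protocol amendment to version 4.0, item A) and two equal groups (12.1), so 3532 / 2 = 1766 per arm.

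**Assumed inputs.** Event proportion per arm of 2%, 5% or 10%, that is 1766 × 0.02 ≈ 35, 1766 × 0.05 ≈ 88 and 1766 × 0.10 ≈ 177 events. There are 5, 10 or 15 conventional predictors, of which five have a log hazard ratio of 0.35 per SD and the rest none. Two imaging variables (CIMT and plaque) have a log hazard ratio of 0 or 0.2 per SD each.

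**Method.** Cox models were fitted in one arm with and without the imaging variables, 150 replicates per setting. Each was evaluated on its own data (apparent) and on 100,000 new subjects (true).

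- Optimism = apparent AUC − true AUC
- Apparent gain = apparent AUC (with imaging) − apparent AUC (without)
- True gain = the same difference in new subjects

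**Results when imaging has no value** (differences come from unrounded means, so the last digit can differ by 0.001):

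| Events | Conventional predictors | Combined, apparent | Combined, true | Optimism, combined | Optimism, without imaging | Apparent gain | True gain |
|---|---|---|---|---|---|---|---|
| 35 | 5 | 0.738 | 0.691 | 0.047 | 0.032 | 0.008 | −0.007 |
| 35 | 10 | 0.756 | 0.671 | 0.085 | 0.070 | 0.009 | −0.006 |
| 35 | 15 | 0.773 | 0.659 | 0.114 | 0.103 | 0.007 | −0.005 |
| 88 | 5 | 0.723 | 0.700 | 0.023 | 0.016 | 0.004 | −0.003 |
| 90 | 10 | 0.733 | 0.693 | 0.040 | 0.034 | 0.003 | −0.003 |
| 87 | 15 | 0.744 | 0.686 | 0.058 | 0.052 | 0.003 | −0.002 |
| 176 | 5 | 0.723 | 0.713 | 0.010 | 0.007 | 0.002 | −0.002 |
| 175 | 10 | 0.727 | 0.709 | 0.018 | 0.014 | 0.002 | −0.002 |
| 176 | 15 | 0.731 | 0.702 | 0.028 | 0.025 | 0.002 | −0.002 |

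**With imaging of real value** (log hazard ratio 0.2 per SD for each variable), optimism of the combined model runs from 0.014 to 0.100. The apparent gain is 0.014 to 0.020 and the true gain 0.008 to 0.015.

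**With both arms pooled** (N = 3532, 5 conventional predictors, imaging of no value), optimism is 0.033 at 72 events and 0.015 at 177 events.

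**Reading the table.**

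1. The combined model shows an apparent AUC of 0.72 to 0.77 although imaging contributes nothing. Only the comparison with the model without imaging reveals this.
2. Whole-model optimism runs from 0.010 to 0.114, driven by events and number of predictors.
3. Most of it is shared by the model without imaging. At 35 events and 10 predictors, 0.085 − 0.070 = 0.015 is left, which equals the apparent gain minus the true gain: 0.009 − (−0.006) = 0.015.
4. So the apparent gain from two worthless variables is only 0.002 to 0.009. It is positive in every setting, while the true gain is slightly negative.

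**The case against.** Section 13.2.3 is a summary, and a detailed plan is said to exist. It may contain a comparator and a validation step. A reader might infer that hypothesis 1 is never tested anywhere; the documents do not support that. What can be said is that no test is described in the Protocol or in SAP Amendment 2. The pointer to Appendix 4 stands in the sentence on the one-year primary outcomes, so it is unknown whether that appendix covers event prediction.

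Nor does the text say that the AUC will be computed on the development data, that all variables enter one model, or that cut-offs or models will be tuned. The listing of CIMT, plaque and risk factors could mean separate models, although the word overall points to a joint one. The phrase "to ensure the highest possible sensitivity and specificity of the predictions" is a loose statement of purpose and describes no procedure. The optimism figures are therefore conditional on the AUC being left uncorrected.

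A reader might also take the whole-model optimism as the size of a spurious imaging gain, or say that the analysis favours hypothesis 1 by construction. Neither follows. The gain from two worthless variables is far smaller, and a combined AUC with no comparator supports neither side. More imaging variables, or selection among them, would be expected to enlarge the gain, but that was not simulated.

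Finally, the analysis is long-term and not primary, and none of the six aims in 6.2 promises a comparison of imaging with a risk score on events. That limits the weight of the point. The mismatch with the first stated hypothesis remains.

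**Conclusion.** The point holds in this form: as described, the event-prediction analysis cannot answer hypothesis 1, because it has no model without imaging and no test of what imaging adds. If the AUC is taken on the development data without correction, it is expected to be too high by about 0.01 to 0.11. The apparent gain from two imaging variables of no value is about 0.002 to 0.009, small but in the direction of the hypothesis.

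These sizes rest on assumed event proportions (2% to 10% per arm), 5 to 15 conventional predictors plus two imaging variables, assumed effect sizes and complete follow-up. The mismatch itself rests on no assumption, only on the text available, which lacks the original SAP. The change should be made, but it concerns a secondary analysis and leaves the randomised comparison untouched.

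**What to change.** In Protocol 13.2.3, or in a SAP amendment before the register events are analysed, replace the single statement on overall predictive ability with two prespecified Cox models for the same events:

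- (a) conventional risk factors, or a conventional score whose outcome matches the endpoint. SCORE was built for fatal CVD (title of Protocol reference 22), while the planned endpoint includes morbidity;
- (b) the same terms plus named baseline CIMT and plaque variables.

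Report the likelihood-ratio test of (b) against (a), and the difference in C-index or time-dependent AUC with a 95% confidence interval. Correct the discrimination of both models for optimism by bootstrap, repeating any variable selection inside each resample. Report calibration, and state the expected number of events and of predictors.

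The nested comparison asks whether imaging adds to the risk model. If the sponsor means imaging in place of it, a third model with imaging alone is needed and compared with (a) by the difference in AUC, since those two are not nested.

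Either pool the arms with stratification by arm or report by arm. The control arm is not an obvious main analysis: it has half the events, and its participants also receive results at three years. State that results were disclosed to the intervention arm at baseline and to everyone at three years (Protocol 9.2.2 and 9.2.4; SAP Amendment 2), and that people with more than 50% stenosis were excluded (10.2.2).

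The cost is a little more analysis code and a lower reported AUC. No new data are needed.
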